12.1.3. Definition of Severity

All AEs will be assessed (graded) for severity and classified using the DMID criteria for grading AEs (Publish date November, 2007; see Appendix 16.1). Any AEs not covered by the DMID criteria will be assessed and classified into 1 of 4 clearly defined categories as follows:

- Mild:** (Grade 1): Transient or mild symptoms; no limitation in activity; no intervention required. The AE does not interfere with the participant's normal functioning level. It may be an annoyance.
- Moderate:** (Grade 2): Symptom results in mild to moderate limitation in activity; no or minimal intervention required. The AE produces some impairment of functioning, but it is not hazardous to health. It is uncomfortable or an embarrassment.
- Severe:** (Grade 3): Symptom results in significant limitation in activity; medical intervention may be required. The AE produces significant impairment of functioning or incapacitation.
- Life-threatening:** (Grade 4): Extreme limitation in activity, significant assistance required; significant medical intervention/therapy required to prevent death, hospitalization; or hospice care probable.

Severity refers to the medical perspective of an event while seriousness reflects the outcome of the event (ie, hospitalization). Events of mild severity can lead to hospitalization and therefore be serious while severe events such as a headache may not meet seriousness criteria.

12.1.4. Definition of Relationship to Study Drug

The investigator or medically qualified designee must review each AE and make the determination of relationship to study drug using the following guidelines:

- Not Related:** The event can be readily explained by other factors such as the subject's underlying medical condition, concomitant therapy, or accident, and no temporal relationship exists between the study drug and the event.

Unlikely:	The event does not follow a reasonable temporal sequence from drug administration and is readily explained by the subject's clinical state or by other modes of therapy administered to the subject.
Possibly Related:	There is some temporal relationship between the event and the administration of the study drug and the event is unlikely to be explained by the subject's medical condition, other therapies, or accident.
Probably Related:	The event follows a reasonable temporal sequence from drug administration, abates upon discontinuation of the drug, and cannot be reasonably explained by the known characteristics of the subject's clinical state.
Definitely Related:	The event follows a reasonable temporal sequence from study drug administration, follows a known or suspected response pattern to the study drug, is confirmed by improvement upon stopping the study drug (dechallenge), and reappears upon repeated exposure (rechallenge, if rechallenge is medically appropriate).

12.1.5. Reporting Serious Adverse Events and Suspected Unexpected Serious Adverse Reactions

Any SAE must be reported by phone or email to the sponsor medical monitor and via the AE and SAE eCRFs within 24 hours of the investigator's awareness of the SAE. All additional follow-up evaluations of the SAE must be reported to BioCryst or its designee as soon as they are available by amending these eCRFs. The SAE notification should be reported to:

Phone (24 hours): [contact]

Email: [contact] and [contact]

In the event the eCRF system is not functioning, the reporting of an SAE **must not** be delayed. Sites will have SAE report forms (electronic Word document) that can be completed and emailed to the above recipients. As soon as the eCRF system is functioning, that particular SAE must be entered into the AE eCRF. The SAE eCRF for that particular event does not need to be completed if the site communicates all follow-up on the separate SAE report form that was initially completed. If the site wishes to enter follow-up information on the SAE via the SAE eCRF, then the SAE eCRF must be completed with the initial as well as the follow-up information.

Immediate reporting should allow BioCryst to take the appropriate measures to address potential new risks in a clinical trial. Therefore, the initial report should be submitted by the investigator within a very short period of time and under no circumstances should this period exceed 24 hours following awareness of the SAE.

The follow-up report should allow BioCryst to determine whether the SAE requires a reassessment of the benefit-risk profile of the study drug in a clinical trial, if the relevant information was not already available and provided in the initial report.

Japan-specific rules and requirements for safety management will be described in the Safety and Medical Management Plan prepared for the current protocol.

BioCryst or its designee will submit all suspected unexpected serious adverse reaction (SUSAR) reports (initial and follow-up) or other safety information (eg, revised IB) to the required authorities.

BioCryst or its designee shall ensure that all relevant information about SUSARs that are fatal or life-threatening is recorded and reported as soon as possible to the competent authorities in all ICH regions, and to the institutional review boards (IRBs) or independent ethics committees (IECs), and in any case no later than 7 days after knowledge by BioCryst of such a case, in accordance with all applicable local laws. All other SUSARs shall be reported to the competent authorities concerned and to the IRBs/IECs concerned as soon as possible but within a maximum of 15 days of first knowledge by BioCryst. BioCryst or designee shall also inform all investigators. Investigators are responsible for retaining a copy in their files, unless otherwise instructed.

12.1.5.1. Reporting Adverse Events of Special Interest

All skin disorders or abnormal findings of the skin are adverse events and should be reported in the usual manner on the eCRF as per Section 12.1.2. However, events of maculopapular rash assessed as related to study drug/IMP, regardless of severity, are considered to be EOSIs which require additional reporting. Any new maculo-papular rash assessed as related to the use of study drug must be reported to the sponsor medical monitor via the eCRFs, specifically both the AE eCRF and the SAE eCRF, within 24 hours of the investigator's *assessment* of the event. The SAE eCRF will also serve as an EOSI Report form, although the rash event itself may not meet seriousness criteria. High resolution photographs must also be submitted via email as described in Section 11.2.14. All additional follow-up evaluations of the event must be reported to BioCryst or its designee as soon as they are available. The notification should be sent to the following email addresses:

Phone (24 hours): [contact]

Email: [contact] and [contact]

In the event the eCRF system is not functioning, the reporting of an EOSI **must not** be delayed. Sites will have SAE/EOSI Report forms (electronic Word document) that can be completed and emailed to the above recipients. As soon as the eCRF is functioning, the EOSI must be entered into the AE eCRF. The SAE eCRF for that particular event does not need to be completed if the site communicates all follow-up on the separate SAE/EOSI Report form that was initially completed. If the site wishes to enter follow-up information on the EOSI via the SAE eCRF, then the SAE eCRF must be completed with the initial as well as the follow-up information.

This method of reporting should allow BioCryst to obtain more information including a full clinical description and information regarding the evaluation. Therefore, the initial report and photographs should be submitted by the investigator within a very short period of time and under no circumstances should this period exceed 24 hours following assessment of the event.

The follow-up report should contain information about the clinical course, medical evaluation, additional photographs (if relevant), biopsy (if done), and laboratory results.

12.1.6. Pregnancy

Any female subject who becomes pregnant during the study should have study drug discontinued immediately and must be followed through the end of the pregnancy. While pregnancy is not considered an AE, all cases of fetal drug exposure via the parent as a study participant (including partners of study participants) are to be reported immediately to BioCryst or its designee.

Consent from a pregnant partner of a study participant will be obtained prior to reporting any details of the pregnancy. Information related to the pregnancy must be given on a “Pregnancy Confirmation and Outcome” form that will be provided by the sponsor or its designee so that the pregnancy may be followed and an outcome determined. Any AEs or SAEs experienced by a pregnant subject are to be reported as directed above in Section 12.1.2 and Section 12.1.5.

Any complications reported in a subject’s pregnant partner should be reported on the Pregnancy Confirmation and Outcome form. All pregnancies must be followed to outcome which occurs when an infant is delivered (live or still born), there is fetal demise, or there is an abortion (spontaneous or induced). Abortion (spontaneous or induced), fetal demise, and still birth along with congenital abnormalities in the newborn, should be reported as separate SAEs.

12.1.7. Serious Breaches of Good Clinical Practice

It is the responsibility of the sponsor to notify the licensing authority of any serious breach of Good Clinical Practice (GCP) that is likely to effect, to a significant degree, the safety or mental integrity of the subjects of the study or the scientific value of the study. All serious breaches will be reported to the relevant competent authority within 7 days. The reporting to the sponsor will be performed by the party who suspects the serious breach.

12.1.8. Treatment Interruptions

Treatment interruptions as a result of investigator management of AEs potentially related to study drug are permissible. Resumption of study drug administration is also permissible upon resolution of the event, as assessed by the investigator, with a plan for stringent monitoring of the subject for recurrence of the AE as appropriate. In addition, other extenuating circumstances may lead to treatment interruptions such as vomiting during an abdominal angioedema event or required fasting for medical procedures; in these cases, study drug should be resumed once the extenuating circumstance is resolved. Treatment interruptions following suspected drug-related rashes are discussed in Section 12.2.1.

The sponsor medical monitor should be notified in the event of a treatment interruption due to an AE. Any treatment interruption will be recorded in the eCRF and source documents, including the reason for the interruption.

12.1.9. Emergency Procedures

Access to study drug/IMP assignment will be available immediately through the IXRS system if the investigator deems it necessary to break the study blind in the interest of a subject’s medical safety, in case of a medical emergency, to meet regulatory reporting obligations, or if warranted during scheduled safety reviews. Where medically appropriate, the investigator will contact the sponsor medical monitor to discuss the situation that has arisen and resulted in the need for unblinding of the subject. The sponsor medical monitor will not be involved in the decision to unblind.

12.2. Adverse Event Management

The investigator (or qualified designee) will grade clinically significant events and laboratory abnormalities according to that detailed in Section 12.1.3. Grade 3 and 4 clinically significant laboratory abnormalities should be confirmed by repeat testing and before any contemplated study drug discontinuation, unless such a delay is not consistent with good medical practice.

In the event that a new clinically significant safety signal emerges, a meeting of the DMC may be convened by the sponsor to evaluate risk to subjects and recommend appropriate actions. Based on the data presented, a decision will be made as to whether to halt the study, to continue dosing, or to continue dosing with provisions introduced into the protocol via substantial amendment.

12.2.1. Rash

Special evaluation of maculopapular drug rash is required as per Section 11.2.14 and special reporting is described in Section 12.1.5.1.

Management of rash should be based on best medical practice and address the subject's presentation. If a subject experiences a Grade 3 or 4 rash suspected to be due to study drug/IMP, the subject should have study drug/IMP dosing stopped immediately as per Section 8.3.2. Grade 3 rashes would include rashes with vesiculation, moist desquamation, or ulceration, and Grade 4 rashes would encompass rashes with mucous membrane involvement or significant exfoliation, erythema multiforme, suspected Stevens-Johnson syndrome, or necrosis requiring surgery.

12.2.1.1. Study Drug Administration for Grade 1 or 2 Rashes Considered Related to Study Drug

Investigators and subjects may elect to continue dosing if the subject experiences a Grade 1 or 2 rash that is deemed related to BCX7353 but the subject is considered to be deriving benefit. By DMID criteria, this reaction would be described as pruritus and/or erythema (Grade 1), or a diffuse maculo-papular rash and/or dry desquamation (Grade 2). In addition, subjects would have to be constitutionally well (no fever, no change in appetite, no malaise, etc), have no mucosal involvement, no vesicles and have no evidence of any hypersensitivity involving the liver or kidney. Mild or moderate eosinophilia may be present but should not prevent continuation of study drug if all other criteria are met. Rash treatment should primarily address symptoms (ie, anti-histamines, topical antipruritics and/or topical corticosteroids). Oral corticosteroids should be avoided, as there is no evidence that oral corticosteroids benefit patients with bland drug-related cutaneous reactions.

If the subject's rash does not improve, or worsens to include vesicles, wet desquamation, or ulceration (Grade 3), then BCX7353 should be immediately discontinued. Subjects who remain on study drug should be followed closely until the rash resolves.

12.2.2. Aminotransferase (ALT or AST) Elevation

All baseline or treatment-emergent ALT or AST elevations $> 3 \times$ ULN (ie, Grade 3 and above) should be confirmed within 72 hours with repeat assessment of ALT and AST as well as total bilirubin, ALP, prothrombin time/INR, and complete blood count for eosinophil levels.

If subjects are asymptomatic with no other pertinent laboratory abnormality, study drug may be continued under close observation with weekly assessment of transaminase levels, total bilirubin, and ALP. These may be done at a local laboratory as long as results are reported to the investigator when available and the investigative site contacts the subject to ascertain any symptoms. If either ALT or AST continue to increase and the subject remains asymptomatic, study drug must be held if:

- Either ALT or AST is $> 5 \times \text{ULN}$ for more than 2 weeks, or
- ALT or AST reaches $> 8 \times \text{ULN}$.

The subject should continue regular assessments of ALT, AST, total bilirubin, ALP, prothrombin time/INR, and complete blood count for eosinophil levels, as deemed appropriate by the investigator, until ALT and/or AST are $< 3 \times \text{ULN}$.

Provided specific criteria are met, the investigator and subject may elect to resume BCX7353 dosing. All of the following criteria must be met for dosing to resume:

- The subject is considered to have been deriving benefit from BCX7353 prior to holding study drug.
- Transaminases return to $\leq 2 \times \text{ULN}$ for subjects whose baseline transaminase levels were above the ULN, and $\leq \text{ULN}$ for those whose baseline transaminase levels were $\leq \text{ULN}$.
- Subjects have not initiated or restarted androgens during the period BCX7353 was held.
- The subject agrees to continue weekly monitoring of ALT, AST, total bilirubin, ALP, complete blood count (eosinophil levels), and prothrombin/INR until levels appear stable and transaminase levels remain $< 3 \times \text{ULN}$ for at least 1 month after restarting BCX7353 dosing.

If at any time, the criteria as outlined in Section 8.3.2 are met, the study drug must be permanently discontinued.

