8.3.2. Subject Discontinuation from Study Drug

A subject will be permanently discontinued from study drug for any of the following reasons, which will be recorded in the source documents and eCRF.

- Emergence of any laboratory abnormality or AE that in the judgment of the investigator compromises the ability of the subject to continue study-specific procedures or it is considered not to be in the subject's best interest due to an altered benefit-risk profile.
- Reoccurrence of treatment-emergent AST or ALT elevation $> 5 \times \text{ULN}$ (confirmed) if BCX7353 is restarted after meeting hold criteria as outlined in Section 12.2.2.
- Treatment-emergent ALT or AST $> 3 \times \text{ULN}$ combined with either laboratory abnormalities indicative of significant hepatic toxicity (ie, meeting Hy's law, total bilirubin $> 2 \times \text{ULN}$ OR with an international normalized ratio [INR] > 1.5) or with symptomatology of acute hepatitis (ie, severe fatigue, nausea, vomiting, right upper quadrant pain and tenderness, fever, rash, and/or eosinophilia [$> 5\%$]).
- Subsequent determination that inclusion/exclusion criteria were not met.
- Intercurrent illness or emergence of a new illness/medical condition that would, in the judgment of the investigator, affect assessments of clinical status to a significant degree.

- Subject noncompliance with study drug or to the protocol.
- The subject has a QTcF > 500 msec (confirmed on repeat ECG testing).
- The subject has a QTcF increase of more than 60 msec (confirmed by repeat ECG) from the mean QTcF value obtained from triplicate ECGs obtained at the baseline visit and a simultaneous absolute QTcF > 450 msec (male) or 470 msec (female).

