- Subjects with a study drug-related Grade 3 or 4 rash as described by the Division of Microbiology and Infectious Diseases (DMID) criteria “skin-mucocutaneous” will be discontinued from study drug and treated according to best medical practice. All subjects with a suspected drug rash should undergo specific rash evaluation as described in Section 12.2.1. A Grade 3 rash is defined as vesiculation or moist desquamation or ulceration and a Grade 4 rash is defined as exfoliative dermatitis, mucous membrane involvement or erythema multiforme or suspected Stevens-Johnson syndrome or necrosis requiring surgery. Subjects with a Grade 1 or 2 study drug-related rash may be continued on BCX7353 if the investigator, subject, and sponsor deem it appropriate. The protocol for continuing BCX7353 in the presence of a rash is described in Section 12.2.1.

Subjects who discontinue from study drug in Parts 1 or 2 will be requested to complete all regularly scheduled visits and procedures outlined in Table 2 and Table 3 through the end of the study part (ie, Part 1 or 2) in which they were currently being treated. Subjects who discontinue in Part 1 will be requested to complete all regularly scheduled visits and procedures through Week 24. Subjects who discontinue in Part 2 will be requested to complete all regularly scheduled visits and procedures through Week 52. Subjects who discontinue in Part 3 will have an EOS visit 3 weeks after the last dose of study drug. All subjects who discontinue from all parts should be treated in accordance with local clinical practice for HAE.

If a subject who discontinues from study drug subsequently withdraws consent to continue study visits as previously outlined, please see Section 8.3.1.

Subjects are not eligible for treatment in Parts 2 or 3 if they discontinue study drug in Parts 1 or 2, respectively due to any of the above cited reasons.

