14.4. Study Termination and Site Closure

Overall, the sponsor may suspend enrollment into the study, suspend treatment of ongoing subjects, or terminate the study to ensure that subjects' safety and welfare are protected.

The entire study, or individual sites, may be terminated for any of the following reasons:

- if the study drug becomes commercially available or another mechanism is available to provide drug to the subject
- changes in scientific knowledge that lead to a negative impact on the benefit-risk profile for subjects
- request of sponsor or competent public authorities/IRB/IEC
- if recruitment cannot be completed in specified time frame
- if the permit to manufacture or import IMP is revoked

The sponsor reserves the right to discontinue the trial prior to inclusion of the intended number of subjects but intends only to exercise this right for valid scientific or administrative reasons. After such a decision, the investigator must contact all participating subjects immediately after notification. As directed by the sponsor, all study materials must be collected and all eCRFs completed to the greatest extent possible.

An individual trial center that is determined to be unsuitable by the sponsor, competent public authorities, or IRB/IEC may be terminated, without affecting the other trial sites.

Except for those situations outlined in Section 8.3, no other formal stopping rules will be defined for individual subjects, parts of the trial, or the entire trial. Individual subjects will be discontinued from the study following the emergence of any laboratory abnormality or AE that in the judgment of the investigator compromises the ability to continue study-specific procedures or is considered not to be in the subject's best interest.

Once BCX7353 receives marketing authorization in Japan, this study will be transitioned to a post-marketing study. Each subject remaining on study may continue to receive access to BCX7353 via this study until such time as BCX7353 is commercially available at his or her study center. Once the last subject is able to access commercial drug product, the study will be terminated.

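### Section 12.2.2 makes both mandatory ALT/AST hold thresholds depend on rising values, so a flat or falling first-episode elevation has no clearly required hold

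*Protocol*

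**What the plan says.** Protocol Section 12.2.2 asks for a repeat within 72 hours of any ALT or AST above 3 x ULN, with bilirubin, ALP, prothrombin time/INR and a blood count for eosinophils. For a subject without symptoms or any other pertinent laboratory abnormality, "study drug may be continued under close observation with weekly assessment of transaminase levels"; that sentence sets no upper level and no time limit.

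The next sentence is the only mandatory hold: "If either ALT or AST continue to increase and the subject remains asymptomatic, study drug must be held if". Two alternatives follow: above 5 x ULN for more than 2 weeks, or reaching above 8 x ULN.

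Section 8.3.2 lists the permanent stops. Three bear on the liver:

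- A confirmed recurrence above 5 x ULN, "if BCX7353 is restarted after meeting hold criteria as outlined in Section 12.2.2".
- ALT or AST above 3 x ULN together with bilirubin above 2 x ULN, INR above 1.5, or symptoms of acute hepatitis.
- A general criterion: "Emergence of any laboratory abnormality or AE that in the judgment of the investigator compromises the ability of the subject to continue study-specific procedures". Its second limb covers a subject whose benefit-risk profile has changed so that continuing is not in his or her best interest.

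Section 12.1.8 adds a permission: "Treatment interruptions as a result of investigator management of AEs potentially related to study drug are permissible". Section 14.4 repeats the general criterion ("Individual subjects will be discontinued from the study following the emergence of any laboratory abnormality or AE that in the judgment of the investigator") and states that no formal stopping rules exist for individual subjects beyond those in Section 8.3.

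**The concern.** The two thresholds look like level triggers, but the clause that introduces them also requires a trend. If the repeat is no higher than the first value, the condition is literally unmet and the permission to continue applies instead, even above 8 x ULN. That level is Grade 4 for ALT and AST in the DMID table in Appendix 16.1. The text gives no reference point for the increase: it could be baseline, screening, the first elevated value or the last test. Two sites could therefore act differently on the same results.

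Other safety rules in Section 8.3.2 carry no trend condition. A QTcF above 500 msec confirmed on repeat requires discontinuation. Subjects with a drug-related Grade 3 or 4 rash "will be discontinued from study drug and treated according to best medical practice". The combined hepatic stop above 3 x ULN also ignores trend. These are permanent stops and not holds, but in each the finding itself is the trigger.

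**Working it through.** No figure in the plan is at issue, so the check is one of logic. It has three steps.

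**1. The rule as written.** Hold required = (ALT or AST continues to increase) AND (asymptomatic) AND (above 5 x ULN for more than 2 weeks OR above 8 x ULN). The five sequences below are invented for illustration, in multiples of ULN. All are a first episode, isolated and asymptomatic. The last column applies the rule without its first condition.

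| Sequence | Days | Threshold met | Rise during observation | Literal hold | Hold without the trend condition |
|---|---|---|---|---|---|
| A: 9.0, 8.8, 8.5 | 0, 3, 7 | above 8 | no | no | yes |
| B: 6.5, 6.4, 6.3, 6.2, 6.0 | 0, 3, 7, 14, 21 | above 5 for 21 days | no | no | yes |
| C: 4, 6, 6, 6, 6 | 0, 7, 14, 21, 28 | above 5 for 28 - 7 = 21 days | yes, then flat | can fairly be read as yes | yes |
| D: 6.5, 6.4, 6.0, 4.5 | 0, 3, 7, 14 | none (above 5 for 7 days) | no | no | no |
| E: 4, 6, 9, repeat 7.9 | not needed | above 8 at the third value | yes | yes, at 9 | yes, at 9 |

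A and B fall in the gap. C and D do not. E is already covered and matters for the wording of the fix.

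**2. Whether another mandatory rule covers A or B.**

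- The recurrence rule in 8.3.2 needs an earlier hold and restart, so it does not reach a first episode.
- The combined hepatic stop needs raised bilirubin, raised INR or symptoms, so it does not reach an isolated value.
- The general criterion in 8.3.2, and its counterpart in 14.4, act only once the investigator has made the judgment.
- Section 12.1.8 permits an interruption and does not require one.

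None of them requires a hold in A or B on the values alone.

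**3. Whether an elevation could first be seen at or past its peak.** The longest gaps between scheduled liver tests, using the visit days and windows in Sections 10.3.3.3, 10.3.4.2 and 10.3.5.1, are:

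- Part 1, Weeks 12 to 18: (127 + 2) - (85 - 2) = 46 days.
- Part 2, Weeks 36 to 48: (337 + 7) - (253 - 2) = 93 days.
- Part 3, Weeks 60 to 72: (505 + 6) - (421 - 6) = 96 days.

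Late first detection is therefore possible. Section 5.3.1 reports one asymptomatic Grade 4 ALT among 40 subjects on 150 mg in Part 1 of Study BCX7353-302: 1/40 = 2.5%. It resolved after study drug was discontinued. Neither its trend nor that study's hold rule is given, so it shows only that values in this range can occur without symptoms.

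**The case against.** The strongest reply is that the gap depends on the narrower of two readings. Section 8.2.2 excludes anyone with ALT or AST at or above 3 x ULN at screening, so a later value above 8 x ULN will normally be a rise since then. The second threshold speaks of reaching a level, and a value first found at 9.0 has reached it. The first threshold is a test of persistence, which suits a sustained elevation. On that reading A and B are covered. This stands as a reading, and it is probably what was intended. It does not settle the matter, because the clause follows directly on the weekly-monitoring sentence and can as naturally mean a rise during that monitoring.

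A trend condition could also be defended on its merits. Section 5.2 reports a mild ALT increase in monkeys that partly resolved while dosing continued, and a hold takes prophylaxis away. That finding was mild and nonclinical, and the protocol does not offer it as a reason for the clause.

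The safeguards are real. Bilirubin and INR are part of the 72-hour repeat, bilirubin is checked weekly, and a hepatic stop without a trend condition applies if they are abnormal. The investigator may stop or interrupt at any time. A reader might infer that a subject with Grade 4 ALT would be kept on drug, or that no hepatic stop works without a trend. The documents support neither inference. What is missing is the requirement to hold, not the ability. Section 12.1.5 also refers to a Safety and Medical Management Plan for Japan-specific safety rules. It is not among the documents and may guide sites on this point.

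**Conclusion.** The point holds as an ambiguity in a safety rule. Read literally, Section 12.2.2 requires no hold for a first-episode, isolated, asymptomatic elevation that meets either threshold but is flat or falling on repeat. Such a case rests on investigator judgment, and no other section requires a hold.

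The conclusion assumes that the increase is counted within the period of observation. If it is counted from screening, the gap largely closes, and the text does not say which is meant. It does not extend to recurrences after restart, to a rise followed by a plateau, or to values above 5 x ULN for 2 weeks or less.

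The frequency cannot be derived, and only about 24 subjects are planned. A reader might take the visit gaps or the Study BCX7353-302 case as evidence of harm. The gaps concern detection only, and that case cannot be placed inside or outside the gap. This is a cheap improvement for patient safety: it could be made, and nothing here shows that it must be.

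**What to change.** In Section 12.2.2, delete the rising-value clause from the mandatory-hold sentence, that is, everything between its opening 'If' and 'the subject'. The hold then applies to any asymptomatic subject who meets either threshold. Leave both threshold bullets unchanged. Begin the preceding sentence, which lets dosing continue, with: 'Unless a hold criterion below is met,'.

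Do not add a requirement that the value above 8 x ULN be confirmed. In sequence E the present text requires a hold at 9. A confirmation requirement could delay that hold by up to 72 hours, and a repeat of 7.9 would remove it under that threshold.

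The cost is an amendment to two sentences and a notice to sites, with no new tests or visits. The downside is that a few subjects with stable or falling values lose prophylaxis until the restart criteria are met. Those criteria include transaminases back to ULN or below if baseline was normal, or to 2 x ULN or below if baseline was raised. A lower dose is not an alternative, because Section 9.5 does not allow dose reductions.
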